### **Duration of Fever**

Duration of fever will be summarized using descriptive statistics, as well as Kaplan-Meier plots. It is defined as the time to return to afebrile state (tympanic temperature  $\leq 37.2^{\circ}\text{C}$ ) and remaining so for at least 21.5 hours.

Patients who do not return to afebrile state will be censored at the last observation time point.

Patients who are afebrile at baseline (tympanic temperature  $\leq 37.2^{\circ}\text{C}$ ) or whose body temperature is not collected will be excluded from the analysis.

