4.3.3 Rescue Medication

If influenza symptoms, such as fever and headache, are so severe, in the opinion of the patient/caregiver, that the patient needs rescue therapy between Day 1 and Day 29, the use of acetaminophen at a dose appropriate to the body weight and age of the child will be permitted only for the relief of fever or pain. If acetaminophen is used, the parent/caregiver will record the use in the patient diary, and the investigator will record the date, time, and dose at the next visit. Acetaminophen will not be provided by the Sponsor.

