4.4.1 Permitted Therapy

Acetaminophen is permitted between Day 1 and Day 29 for severe influenza symptoms at a dose appropriate to the body weight and age of the child. See Section 4.3.3 for further details.

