### **Time to Alleviation of Influenza Signs and Symptoms**

Time to alleviation of influenza signs and symptoms (TTAS) in hours, will be summarized using descriptive statistics, as well as Kaplan-Meier plots. It is defined as the length of time taken from the start of treatment to the point at which all of the following criteria are met and remain so for at least 21.5 hours:

- A score of 0 (no problem) or 1 (minor problem) for cough and nasal symptoms (items 14 and 15 of the CARIFS questionnaire, see [Appendix 4](#)).
- A “yes” response to the following question on the CARIFS: “Since the last assessment has the subject been able to return to day care/school, or resume his or her normal daily activity in the same way as performed prior to developing the flu?”
- Return to afebrile state (tympanic temperature  $\leq 37.2^{\circ}\text{C}$ ).

If a score of 4 (“Don’t Know/Not Applicable”) occurs at any assessment during the study for items 14 or 15, the assessment will not be included in the calculation of the alleviation of symptoms because the assessment was unobservable.

Patients with symptom scores  $\leq 1$  for both items 14 and 15, as well as tympanic temperature  $\leq 37.2^{\circ}\text{C}$  and a “yes” response to the question “Since the last assessment has the subject been able to return to day care/school, or resume his or her normal daily activity in the same way as performed prior to developing the flu?” simultaneously at baseline will be excluded from the analysis.

Patients who do not experience alleviation of symptoms prior to completion or withdrawal from study will be censored at the last observation time point.

Baseline is defined as the first CARIFS assessment on Day 1 after the start of treatment. Patients who do not have a CARIFS assessment on Day 1 after the start of treatment will have their baseline CARIFS assessment set to missing.

The number of patients with completed CARIFS as well as the number with missing CARIFS per assessment will be presented for the ITT and ITTi sets. Additionally, the number and percentage of those with “Don’t Know/ Not Applicable” per question per assessment will be presented for the ITT and ITTi sets.

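### Fever endpoints count readings at or below 37.2 °C toward the 21.5-hour afebrile period regardless of recent acetaminophen, although its use and timing are recorded

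*SAP*

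**What the plan says.** **Duration of Fever (SAP 4.3.1).** "It is defined as the time to return to afebrile state" at a tympanic temperature of 37.2 °C or below, "and remaining so for at least 21.5 hours". On censoring, the section says: "Patients who do not return to afebrile state will be censored at the last observation time point". Infants afebrile at baseline, or with no temperature collected, are left out of the analysis.

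**TTAS (SAP 4.3.1), the key secondary endpoint.** "Return to afebrile state" at the same threshold is one of three criteria. The others are cough and nasal scores of 0 or 1 and a positive answer to the normal-activity question. All must hold together for at least 21.5 hours. The two sensitivity analyses concern the don't-know/not-applicable score and removal of the activity question.

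**Baseline temperature (SAP 4.2.1.5).** This is the first Day 1 reading after study treatment, with no condition on antipyretic use.

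**Acetaminophen.** "Acetaminophen is permitted between Day 1 and Day 29 for severe influenza symptoms" (Protocol 4.4.1). Protocol 4.3.3 limits it to relief of fever or pain and adds that "the parent/caregiver will record the use in the patient diary, and the investigator will record the date, time, and dose at the next visit".

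**Other handling.** SAP 4.3.1 rules out imputation beyond what it describes for TTAS, and none of that concerns acetaminophen. SAP 4.5.1 gives concomitant treatment a descriptive summary that is not linked to the fever endpoints.

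**The concern.** Acetaminophen is given in response to fever and lowers the quantity that defines the endpoint. A reading of 37.2 °C or below soon after a dose may reflect the antipyretic rather than the end of the febrile illness. The SAP makes no such distinction: every qualifying reading counts toward the afebrile period.

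In a controlled trial a comparison arm would share at least part of this effect. Here there is one arm, so the reported fever duration includes whatever the antipyretic contributes and nothing in the planned output lets a reader separate it. With about 30 infants, and fever no longer required for entry, the fever analysis set may be small, and a few shifted times could move a Kaplan-Meier median.

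**Working it through.** The plan states no figure on this point, so there is none to reproduce. The check compares the rules and then counts readings.

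**Inputs**
- Threshold of 37.2 °C and 21.5-hour hold: SAP 4.3.1.
- Temperature schedule: four times daily on Days 1 to 3, twice daily on Days 4 to 9, once daily on Days 10 to 15 (Protocol 3.1).
- Recording periods: morning 05:00–10:59, noon 11:00–14:59, evening 15:00–18:59, bedtime 19:00–23:59 (SAP Table 4).
- Assumed nominal times inside those periods: 08, 13, 17 and 21 h; 08 and 17 h when twice daily; 08 h when once daily.
- Assumed reading of the definition: the event time is the first reading of an unbroken afebrile run whose last reading is at least 21.5 hours later.

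**1. Readings needed to span 21.5 hours**
- Days 1 to 3: 08, 13, 17, 21, 08 = five readings over 24 h. At the extreme edges of the recording periods four can suffice, for example noon at 11:00 to next morning at 10:59, which is 23 h 59 min.
- Days 4 to 9: 08, 17, 08 = three readings over 24 h. Two in succession cannot do it unless one is missing: evening at 15:00 to next morning at 10:59 is 19 h 59 min.
- Days 10 to 15: 08, 08 = two readings over 24 h.

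**2. One masked reading just before true resolution.** The event moves forward by one reading interval.
- Days 1 to 3: 13−8 = 5 h, 17−13 = 4 h, 21−17 = 4 h, 21 to 08 = 11 h.
- Days 4 to 9: 17−8 = 9 h, 17 to 08 = 15 h.
- Days 10 to 15: 24 h.

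As a yardstick, Protocol 1.2.4 gives a median time to resolution of fever of 21.4 h in the Japanese pediatric study. For a single infant, 4/21.4 = 19% and 11/21.4 = 51% on Days 1 to 3; 9/21.4 = 42% and 15/21.4 = 70% on Days 4 to 9. These are shifts in one infant's time, not in the study median.

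**3. A wholly false resolution.** All k readings of a still-febrile infant must be masked. If each is masked with probability p, independently, the chance is p^k. The documents give no p, so a range is shown.

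| k | p = 0.25 | p = 0.50 | p = 0.75 | p = 0.90 |
|---|---|---|---|---|
| 5 | 0.001 | 0.031 | 0.237 | 0.590 |
| 3 | 0.016 | 0.125 | 0.422 | 0.729 |
| 2 | 0.0625 | 0.250 | 0.5625 | 0.810 |

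With occasional dosing and frequent readings, the hold removes most false resolutions. With repeated dosing or sparse readings it does not. Repeated dosing makes masked readings cluster, so independence probably understates the chance.

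**4. TTAS.** The main analysis uses only assessments with the cough and nasal items, the activity answer and temperature all present, and CARIFS is scheduled twice daily on Days 1 to 9. The hold therefore rests on about three assessments even on Days 1 to 3. Masking changes TTAS only when fever is the last criterion to resolve.

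**5. Baseline.** If the first reading after study treatment is masked, a febrile infant is classed as afebrile and dropped from Duration of Fever. The effect on the summary depends on how long that infant's fever would have lasted, so its direction is unknown.

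**The case against.** Much of the case against stands, and it limits the point.

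- **The hold.** A reader might infer that any single low reading counts as resolution. It does not: a dip followed by a febrile reading inside the 21.5 hours is not an event. On Days 1 to 3, where the 21.4 h yardstick falls, about five readings are needed.
- **TTAS.** A reader might infer that masking passes straight into the key secondary endpoint. The pediatric study in Protocol 1.2.4 had a median of 21.4 h for fever and 44.6 h for alleviation of illness. Definitions differ, but fever may often not be the limiting criterion.
- **Direction.** A reader might infer that the bias always favours the drug. For infants in the analysis, masking can only bring the event earlier, but the baseline exclusion can act either way.
- **Existing restraints.** Acetaminophen is reserved for severe symptoms, other antipyretics are prohibited, and concomitant treatment is summarized. These may reduce masking, but none shows its effect on the fever results.
- **Data quality.** The investigator enters date, time and dose at the next visit. Mandatory visits are on Days 2, 4, 6, 10 and 29, so clock times may be entered days later.
- **The alternative has its own bias.** Acetaminophen is also allowed for pain, so refusing readings after a dose would lengthen duration for some recovered infants. Counting observed temperature regardless of rescue is a legitimate main analysis.

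The last two points are reasons to make this a sensitivity analysis rather than a replacement. They do not justify leaving the recorded data unused.

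**Conclusion.** The point holds in a limited form. Readings at or below 37.2 °C count toward the afebrile period whatever the recent acetaminophen use, and no planned analysis shows whether the results depend on that.

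The overall size cannot be computed, because the frequency and timing of use are unknown. At the assumed reading times, one masked reading at the start of the run moves an infant's event by 4 to 11 h on Days 1 to 3 and 9 to 15 h on Days 4 to 9. A shift of about a day from masking alone is the extreme case while readings are taken two or four times daily: it needs every reading in a minimum-length run to be masked, and should not be read as typical.

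The consequence is confined to descriptive secondary endpoints. There is no hypothesis test, so no error rate or sample size is affected, and the primary safety objective does not depend on these endpoints. It is a modest gap that is cheap to close.

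**What to change.** Leave the main analyses of Duration of Fever and TTAS as they are. Add to SAP 4.3.1:

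1. One sensitivity analysis for both endpoints in which a temperature taken within a pre-specified interval after recorded acetaminophen is not accepted as afebrile. It can neither start nor continue the 21.5-hour run, and at baseline it does not classify the infant as afebrile. Show it for two intervals, for example 4 and 6 h. Both are analysis assumptions, not values from the documents.
2. A table of the number and share of infants using acetaminophen, by study day.

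The SAP should also say what happens when a dose has no usable clock time. For the baseline rule, it should say whether acetaminophen taken before study treatment counts. Protocol 4.5.2 has prior medication recorded but does not mention clock time.

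**Cost.** One extra analysis and one table on data already collected, with no change to rescue use or any clinical rule. The result will depend on the accuracy of dosing times entered at the next visit and on the chosen interval, and it may overstate duration for recovered infants dosed for pain. State these limits beside the output.

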### **Duration of Symptoms**

Duration of symptoms will be summarized using descriptive statistics, as well as Kaplan-Meier plots. Duration of symptoms is defined as alleviation of all symptoms as defined by a score of 0 [no problem] or 1 [minor problem] and remaining so for at least 21.5 hours, for all 18 symptoms specified in the CARIFS questionnaire.

If a score of 4 (“Don’t know/Not Applicable”) occurs at any assessment during the study for any item, with the exception of items 10, 11, and 12, the assessment will not be included in the calculation of the duration of symptoms because the assessment was unobservable.

However, if a score of 4 occurs for items 10, 11, or 12, the assessment will be included, with a score of missing for these items.

All patients will be included in the analysis, regardless of their symptoms at baseline.

In addition, duration of individual symptoms will be summarized using descriptive statistics, as supportive analysis, with the exception of items 10, 11, and 12. If a score of 4 (“Don’t know/Not Applicable”) occurs for the individual symptom at any assessment during the study the assessment will not be included in the calculation of the duration of that individual symptom. Patients who have an individual symptom score  $\leq 1$  at baseline will have the duration of that symptom set to missing.

In the main analysis of the duration of symptoms, only complete assessments (i.e., assessments that have responses for all 18 symptoms in the CARIFS questionnaire) that do not contain a score of 4 for any items, with the exception of items 10, 11, and 12, are considered. A sensitivity analysis will be conducted that considers all assessments in the calculation of the duration of symptoms, where a score of 4 does not break the

incidence of alleviation for items other than 10, 11, and 12, and a score of 4 is considered alleviation for items 10, 11, and 12.

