4.1.1 Inclusion Criteria

Patients must meet the following criteria for study entry:

- Written informed consent for study participation obtained from patient's parents or legal guardian
- Age from birth to <1 year at screening
- Parent/guardian willing and able to comply with study requirements, in the investigator's judgment
- Patients with a diagnosis of influenza virus infection confirmed by the presence of **all** of the following:
 - *In the investigator's judgement there is a clinical suspicion of influenza*
 - At least one respiratory symptom (either cough or coryza)
 - Positive prescreening influenza test (RIDT or PCR) performed within *48 hours of screening*

Results from local testing as part of standard of care are acceptable if samples are collected within 48 hours of screening and recorded in the patients' medical records.

- Patients with a negative prescreening COVID-19 test (*RAT or PCR*) *within 48 hours of screening*

Results from local testing as part of standard of care are acceptable if samples are collected within 48 hours of screening and recorded in the patients' medical records.
- The time interval between the onset of symptoms and screening is ≤ 96 hours (the onset of symptoms is defined as the time when body temperature first exceeded 37.5°C if known, or the time when the first symptom was noticed by the parent or caregiver)

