## **1.2 STUDY DESIGN**

This is a multicenter, single-arm, open-label study to assess the safety, pharmacokinetics, and efficacy of baloxavir marboxil in otherwise healthy pediatric patients from birth to <1 year with influenza-like symptoms. This study is designed to enroll approximately 30 otherwise healthy male and female pediatric patients with influenza-like symptoms presenting within 96 hours of symptom onset.

Patients will be screened on Day 1 and assigned to receive a single oral dose of baloxavir marboxil according to body weight and age, as defined below.

Patients will be recruited in parallel to the following three cohorts:

- **Cohort I:**  $\geq 3$  months to <12 months old (minimum 8 patients): 2 mg/kg
- **Cohort II:**  $\geq 4$  weeks to <3 months old (minimum 4 patients): 1 mg/kg
- **Cohort III:** birth to <4 weeks old (minimum 3 patients): 1 mg/kg

The study consists of two periods: a 1-day treatment period and a 28-day safety follow-up period. Therefore, the total study duration for each patient will be 29 days.

The Study CP40559 protocol synopsis is provided in [Appendix 1](#). For additional details, see the Schedule of Assessments in [Appendix 2](#) and [Appendix 3](#).

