## Appendix 4 Canadian Acute Respiratory Illness and Flu Scale (CARIFS) Questionnaire

Item	No Problem	Minor Problem	Moderate Problem	Major Problem	Don't Know/Not Applicable
1. Poor appetite					
2. Not sleeping well					
3. Irritable, cranky, fussy					
4. Feels unwell					
5. Low energy, tired					
6. Not playing well					
7. Crying more than usual					
8. Needing extra care					
9. Clinginess					
10. Headache					
11. Sore throat					
12. Muscle aches or pains					
13. Fever					
14. Cough					
15. Nasal congestion, runny nose					
16. Vomiting					
17. Not interested in what's going on					
18. Unable to get out of bed					

Since the last assessment has the subject been able to return to day care/school, or resume their normal daily activity in the same way as performed prior to developing the flu?  Yes  No

This form was filled out by:

- Parent
- Carer
- Other

Note: The term "Carer" in this questionnaire corresponds to the term "caregiver" used throughout the protocol.

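### Duration of symptoms: a Not Applicable answer is tolerated only on CARIFS items 10–12, so an infant consistently marked Not Applicable on item 18 (or item 6) has no usable assessment in the main analysis

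*SAP*

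**What the plan says.** The SAP (4.3.1, Duration of Symptoms) requires a score of 0 or 1 on all 18 CARIFS items, sustained for at least 21.5 hours. A score of 4 is the single response for Don't Know/Not Applicable. For a 4 on any item, "with the exception of items 10, 11, and 12, the assessment will not be included in the calculation of the duration of symptoms". For the three exempt items the rule differs: "if a score of 4 occurs for items 10, 11, or 12, the assessment will be included, with a score of missing for these items". The main analysis is then restated as using only complete assessments "that do not contain a score of 4 for any items, with the exception of items 10, 11, and 12, are considered".

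A second analysis is planned: "A sensitivity analysis will be conducted that considers all assessments in the calculation of the duration of symptoms, where a score of 4 does not" interrupt alleviation on items other than 10, 11 and 12, while a 4 on items 10–12 counts as alleviation. Durations of individual symptoms are also summarised. The SAP says every patient is included whatever the baseline symptoms, and 4.3.1 rules out further imputation beyond that described for time to alleviation of signs and symptoms (TTAS).

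The questionnaire (SAP Appendix 4) contains "6. Not playing well" and "18. Unable to get out of bed". Eligibility (Protocol 4.1.1) is "Age from birth to <1 year at screening", and the youngest cohort (SAP 1.2) is "birth to <4 weeks old (minimum 3 patients): 1 mg/kg". Protocol 4.5.6 asks for the questionnaire to be filled in completely and leaves data-handling conventions to the SAP. Neither document tells caregivers how to answer an item that does not fit the infant's age.

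**The concern.** The SAP already accepts that some items cannot be scored at this age and that such an item should not cost the rest of the assessment. It applies this to symptoms an infant cannot report. It does not apply it to items describing something a young infant does not do. No newborn gets out of bed, ill or well, and play is hard to judge in the first weeks of life. If the caregiver marks such an item Not Applicable, the answer will probably be the same at every entry, including after full recovery. The rule then discards entries in which every other item was observed.

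At stake is whether the youngest infants contribute to a stated secondary efficacy endpoint. Any loss would follow age, and the two cohorts under 3 months are also those assigned 1 mg/kg. It would not be a random thinning of the data.

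**Working it through.** The plan gives no figure to reproduce, and no test or sample-size formula applies. The check applies the rule literally to the diary schedule.

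**Inputs**
- Schedule (Protocol 3.1 and Appendix 1): CARIFS twice daily on Days 1–9, once daily on Days 10–15.
- Exempt items: 10, 11, 12. Non-exempt: 18 − 3 = 15 items, including 6 and 18.
- Cohort minima (SAP 1.2): 8, 4 and 3; planned total about 30.

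**Step 1. Scheduled assessments per infant:** 2 × 9 + 1 × 6 = 24.

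**Step 2. Assessments kept when an item is scored 4 throughout**

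| Items always scored 4 | Kept in main analysis |
|---|---|
| none | 24 of 24 |
| 10, 11 and 12 | 24 of 24 |
| 18 only | 0 of 24 |
| 6 only | 0 of 24 |
| 10, 11, 12 and 18 | 0 of 24 |

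**Step 3. Intermittent use.** The documents do not give the share r of assessments with a 4 on item 6 or 18, so r is an assumption. The expected number kept is 24 × (1 − r): 18 at r = 0.25, 12 at 0.50, 6 at 0.75, 2.4 at 0.90 and 0 at 1.0.

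**Step 4. Infants most exposed.** The minima for the two cohorts under 3 months sum to 4 + 3 = 7, and 7/30 = 23%. Under 4 weeks alone it is 3/30 = 10%. These are enrolment minima, not forecasts of how many caregivers will answer this way.

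**Step 5. Does the sensitivity analysis recover such an infant?** Its wording treats two groups of items differently. On items 10–12 a 4 is alleviation. On the others a 4 only fails to interrupt alleviation. If that means a 4 is neutral from the start, the infant is recovered. If it means that an alleviation period already begun is not ended, an item scored 4 throughout never reaches 0 or 1 and the period never begins. The text does not settle which is meant.

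**Step 6. What happens to an infant with nothing usable?** In SAP 4.3.1, TTAS, duration of fever and return to normal activity each have a rule censoring patients without the event at the last observation. Duration of Symptoms has none. The general sentence in 4.3.1 covers only patients who withdraw. For an infant who completes the study with every assessment excluded, it is undefined whether the censoring time is the last diary entry, time 0, or whether the infant leaves the analysis.

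**The case against.** The strongest reply is that the premise is not in the documents. CARIFS asks about problems, and a caregiver of a newborn may simply tick No Problem for getting out of bed; that assessment is kept. Neither document says that items 6 or 18 are inapplicable in infancy, or reports how caregivers answer them. This stands, and it makes the loss a possibility rather than an expected result.

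The plan also has safeguards. Counts of Don't Know/Not Applicable per question and assessment are tabulated (SAP 4.3.1, under TTAS), individual symptom durations limit the effect of a 4 to that item, and a sensitivity analysis uses all assessments. The tabulation would expose the problem but not correct the main estimate, and the sensitivity analysis is ambiguous as shown in Step 5.

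The stakes are limited. The study is single-arm and descriptive, no efficacy comparison between dose levels is planned, and TTAS uses only items 14 and 15, the activity question and temperature.

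A reader might go further and infer that the reported median will be inflated by a calculable number of hours. The documents do not support that. Inflation requires affected infants to be carried as event-free to the end of the diary at Day 15, a convention not stated for this endpoint. Dropping them, or censoring them at time 0, gives no such inflation.

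Finally, Don't Know and Not Applicable share one code, so any wider exemption also ignores some genuine Don't Know answers. This is a reason to keep the list short: exempting play for older infants, or clinginess (item 9) and interest in surroundings (item 17) in the youngest, is debatable.

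**Conclusion.** The point holds as a gap in the main-analysis rule, not as a demonstrated bias. One persistent Not Applicable on item 18 or item 6 takes an infant from 24 usable assessments to 0, whereas the same answer on items 10–12 costs nothing. The infants most exposed are those under 3 months, at least 7 of about 30 if the cohort minima are met. How many would actually be lost depends on caregiver behaviour that the documents do not describe. Neither the certain loss of the youngest infants nor a specific shift in the median can be claimed. The missing censoring rule for completers adds to the problem, because it leaves the treatment of such infants to be decided after the data are seen. Since the endpoint is secondary and descriptive and TTAS is unaffected by these items, this is a change that should be made; it does not undermine the study's main conclusions.

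**What to change.** Before database lock, amend SAP 4.3.1, Duration of Symptoms:

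1. Extend the item 10–12 handling (a 4 set to missing, assessment kept) to a pre-specified, age-based list: at least item 18 for all infants and item 6 for infants under 3 months. Require 0 or 1 on all remaining items.
2. Keep the current rule as a sensitivity analysis. For the existing all-assessments analysis, state whether an item scored 4 throughout can begin an alleviation period.
3. State the censoring time for an infant who completes the study without the event, and for one with no usable assessment.

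The cost is SAP wording and a small programming change. No change to data collection is needed, and the exemption acts only when a 4 is recorded, so real scores on these items still count. The downside is that alleviation is judged on one or two fewer items in some infants, and a true Don't Know on those items is also ignored. Reporting both rules side by side shows how much this matters.
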